## 12.3 Sample Size Determination

We aim to recruit a maximum of 1060 patients (for 90% power, 530 per arm), with a minimum of 792 (for 80% power, 396 per arm) women from at least 30 NHS centres. UK-based registry data indicates that ~45% of women with tumours >2cm undergo mastectomy; based on discussions with patient representatives and confirmed at the NCRI Dragons Den, we consider a reduction of 10% (i.e. mastectomy rate reduced from 45% to 35% resulting in BCS rate increase from 55% to 65%) to be clinically meaningful to patients and lead to a change in clinical practice.

EndoNET\_Protocol\_V4.0\_21Aug2024

© Copyright: The University of Oxford and Oxford University Hospitals NHS Foundation Trust 2022 Page 63 of 84

The sample size of 1060, and 792, would allow us to detect this difference with 90% and 80% power respectively at a two-sided 5% significance level allowing for a cross-over and attrition at 15 months up to 5%.5% is based on loss to follow up experienced for the clinical endpoints in the iBra study.

80% power is considered to be sufficiently robust and in line with other similar and recent trials (104, 105). However, if recruitment to 1060 (for 90% power) seems achievable, given the observed recruitment trajectory, then the DSMC and TSC will be contacted to consider continuation of recruitment to 1060 patients.

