## 9.6. Randomisation (Main Trial)

We will randomise eligible patients using the centralised validated computer randomisation program through a secure (encrypted) web-based service, RRAMP (https://rramp.octru.ox.ac.uk), provided by the Oxford Clinical Trials Research Unit (OCTRU), accessed via the study's REDCap instance, with a minimisation algorithm to ensure balanced allocation across treatment arms, stratified in a 1:1 ratio to either NET followed by standard of care or standard of care using:

- Age group (<60, 60-70, 70+ years);
- Nodal status (N0 vs N1 or N2);
- Recruiting centre, and
- Surgical indication at baseline (BCS vs mastectomy)

To ensure the unpredictability of treatment allocation the minimisation algorithm will include a probabilistic element and a small number of participants randomised by simple randomisation. Stratification by centre will help to ensure that any centre-effect will be equally distributed in the trial arms and enable practical issues associated with the active intervention to be overcome. In the unlikely event that the randomisation system is down for any reason, if delays in randomisation occur to such an extent that they impact treatment planning felt to affect the prognosis of the participant, then they will be withdrawn and returned to the usual standard of care pathway if deemed necessary by the treating clinician. For participants who do not wish to or who are unable to comply with their randomisation outcome (according to the investigator and/or clinical team), they will continue to participate in the study but will be analysed on an intention to treat basis.

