## 9.18. Definition of crossover

Crossover in this trial is defined as:

- When a participant who is randomised to the comparator arm's first surgery is late (e.g. anaesthetic review being unfit for surgery may be a reason for this)
- When a participant who is randomised to the NET arm has early surgery.

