#### 12.4 Analysis of Trial Populations by Intention to Treat

The principal analysis will be performed on the intention-to-treat population, analysing with participants with available outcome data in their randomised groups, regardless of adherence.

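### Section 12.3 says the 80% and 90% power allow for cross-over, but 792 and 1060 contain only a 5% loss-to-follow-up inflation

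*Protocol*

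**What the plan says.** Section 12.3 of the protocol gives two sizes: a "maximum of 1060 patients (for 90% power, 530 per arm") and "with a minimum of 792 (for 80% power, 396 per arm) women". The effect is a "mastectomy rate reduced from 45% to 35% resulting in BCS rate increase from 55% to 65"%, to be detected "with 90% and 80% power respectively at a two-sided 5% significance level". The sizes are described as "allowing for a cross-over and attrition at 15 months up to 5%.5% is based on loss to follow up" in an earlier study of breast reconstruction. One figure of 5% thus serves for both cross-over and attrition, and its only stated source is loss to follow-up. The protocol gives no planning rate for cross-over.

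Section 9.18 defines cross-over by the timing of surgery. In the intervention arm it is "When a participant who is randomised to the NET arm has early surgery"; in the comparator arm it is a late first operation. Section 9.17 foresees early surgery for progression on NET. Table 1 in section 5.2 foresees it for women who cannot tolerate endocrine therapy. Section 6.2 lists the cross-over rate as a secondary outcome.

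Section 12.4 sets the principal analysis as intention to treat, "analysing with participants with available outcome data in their randomised groups, regardless of adherence".

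**The concern.** Attrition and cross-over harm power in different ways. A woman lost to follow-up leaves the analysis, so the number analysed falls and the expected difference stays the same. A woman who crosses over stays in her randomised group under section 12.4, so the number stays the same and the expected difference shrinks. To allow for both, a plan needs a rate for each and an assumption about how much of the effect a crossed-over woman keeps. Section 12.3 gives one rate, sourced to attrition alone, and says that it covers both.

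The minimum of 792 is justified by its 80% power. Section 12.3 also foresees asking the DSMC and TSC to consider continuing to 1060. Both committees should know the power at each size once cross-over is counted.

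**Working it through.** **Inputs.** Breast conservation 55% (control) and 65% (NET), two-sided 5% significance, 80% and 90% power, 396 and 530 per arm (all section 12.3). Allocation 1:1 (section 9.6). The protocol states no cross-over rate, so the rates below are assumptions.

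**Step 1: reproduce the stated sizes.** The pooled-variance formula for two proportions, without continuity correction, is

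n per arm = [1.96 × √(2 × p̄ × (1 − p̄)) + z × √(p₁(1 − p₁) + p₂(1 − p₂))]² / (p₂ − p₁)²

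with p₁ = 0.55, p₂ = 0.65, p̄ = 0.60, and z = 0.842 for 80% power or 1.282 for 90%.

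- 80%: 375.6, rounded up to 376; 376 / 0.95 = 395.8, rounded up to 396 per arm, 792 in total.
- 90%: 502.3, rounded up to 503; 503 / 0.95 = 529.5, rounded up to 530 per arm, 1060 in total.

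Both stated sizes are matched exactly. Other constructions do not match both. The continuity-corrected formula without attrition gives 792 and 1046, the continuity-corrected formula with attrition gives 834 and 1102, and unpooled variance with attrition gives 786 and 1054. The only inflation present is therefore one division by 0.95.

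**Step 2: margin at the planned attrition.** With 5% lost, 396 × 0.95 = 376.2 and 530 × 0.95 = 503.5 women per arm are analysed. Power is 80.07% and 90.07%, so almost nothing is left over.

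**Step 3: add cross-over.** Let c be the proportion of the NET arm who cross over and r the share of the 10-point effect that such a woman keeps. Under intention to treat the expected NET rate is

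p_NET = 0.65 − 0.10 × c × (1 − r)

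For example, c = 5% gives 0.645 with r = 0 (a crossed-over woman has the control rate) and 0.6475 with r = 0.5. Power is then computed from the same formula at 396 × (1 − attrition) and 530 × (1 − attrition) per arm.

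| Attrition | NET cross-over | Power at 792 / 1060, r = 0 | Power at 792 / 1060, r = 0.5 |
|---|---|---|---|
| 5% | 0% | 80.1% / 90.1% | 80.1% / 90.1% |
| 2.5% | 2.5% | 79.0% / 89.3% | 80.1% / 90.1% |
| 0% | 5% | 77.9% / 88.5% | 80.1% / 90.1% |
| 5% | 2.5% | 78.0% / 88.5% | 79.1% / 89.3% |
| 5% | 5% | 75.8% / 86.8% | 78.0% / 88.5% |
| 5% | 10% | 71.1% / 83.0% | 75.8% / 86.8% |

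Rows 2 and 3 keep within a combined ceiling of 5%, which is the most natural reading of the sentence in section 12.3. The last three rows go beyond it, because they add cross-over to the full 5% attrition.

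**Step 4: why half retention matters.** The required n grows by about 1 / (1 − c(1 − r))². With c = 5% and r = 0.5 that is 1 / 0.975² = 1.052, and 1 / 0.95 = 1.053, so dividing by 0.95 is just enough. With r = 0 it is 1 / 0.95² = 1.108, and dividing by 0.95 covers about half of what is needed.

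**The case against.** The best defence is that a larger sample does offset dilution, so one inflation could serve for both. Step 4 shows that this works if crossed-over women keep half the effect: any mix of cross-over and attrition up to 5% in total then meets 80% and 90%. Partial retention is plausible, because section 9.18 defines cross-over by timing, both arms start an aromatase inhibitor at randomisation, and one series cited in section 5.1 reports 60% conversion to conservation at 3 months against 72% eventually. Women who cross over because of progression would probably keep little. The defence limits the size of the shortfall, but the protocol does not state the assumption it needs and sources the 5% to loss to follow-up.

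A second defence is that the 10 points may already be the intention-to-treat effect, net of cross-over. Section 12.3 does not say so. It presents 10 points as the clinically meaningful difference and then claims an allowance on top. If 10 points were net, the reference to cross-over would be redundant.

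A third defence is that the planned mixed logistic model (section 12.2) adjusts for clinical stratification factors, which include the surgical indication at baseline, probably a strong predictor of breast conservation. Adjustment may well recover power. Section 12.3 claims no such gain and gives no figure from which to compute one. The point stands that the powers above are for the unadjusted comparison.

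Three stronger readings are tempting but not supported:

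- A reader might infer that the stated power is lost as soon as anyone crosses over. That holds only if attrition uses the full 5%. With no attrition, 2.5% NET cross-over with nothing retained still gives 80.05% at 792 and 90.05% at 1060.
- A reader might infer that true power is near 71% and 83%. Those figures need 10% NET cross-over with nothing retained, or a full swap of 5% in each arm, on top of 5% attrition. The protocol states no such rates, and a comparator operation that is merely late does not confer six months of NET.
- A reader might infer that the trial must be enlarged, to 880 or 1176 for 5% attrition and 5% undiluted NET cross-over. The documents do not establish that rate.

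**Conclusion.** The point stands as an error in the stated basis of the sample size. Section 12.3 claims an allowance for cross-over that its own figures do not contain, since 376 / 0.95 and 503 / 0.95 account for both sizes in full and the 5% comes from attrition alone.

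The likely size is modest. Within a combined 5% ceiling, and if crossed-over NET women have the control rate, the shortfall is about 1 to 2 points (79.0% to 77.9% at 792, 89.3% to 88.5% at 1060). With 5% of each it is about 4 points at 792 (75.8%) and 3 at 1060 (86.8%). With half the effect retained, the shortfall disappears within the ceiling and is about 2 points with 5% of each. All these figures rest on assumed rates, on cross-over in the NET arm only, and on the unadjusted comparison. They do not show that the trial is materially underpowered. They show that the protocol does not support its claim about cross-over.

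**What to change.** In section 12.3, take cross-over out of the 5% allowance, so that 80% at 792 and 90% at 1060 are stated as allowing for 5% attrition only. Add a short table of power at both sizes by assumed NET cross-over rate (for example 0%, 2.5%, 5% and 10%). State the share of the effect that crossed-over women are assumed to keep, and note that the figures are for the unadjusted comparison. When continuation to 1060 is considered, update the table with the cross-over rate observed to date, pooled over arms.

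The cost is a change of protocol wording and a slightly less favourable statement of power. The sample sizes, the endpoint, the analysis and patient management stay as they are, and no extra patients are needed.

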#### 12.4 Analysis of Trial Populations by Intention to Treat

The principal analysis will be performed on the intention-to-treat population, analysing with participants with available outcome data in their randomised groups, regardless of adherence.

#### 12.5 Stopping Rules

No formal interim comparative analyses are anticipated prior to completion of follow-up for the designated time points. The DSMC may request interim analyses at any point in the trial, which will be performed by the trial statistician. A DSMC charter will be in place for the EndoNET trial.

#### Internal Trial Pilot

Formal stop/go review will be at the end of the trial pilot, which took place on 31st December 2023 to ensure 12 sites opened and 150 patients were randomised.

Target	Actual recruitment at end of trial pilot				
	>150 participants	100-150	<100 participants		
Stop-Go Criteria	
 
Recruitment feasible
 
Proceed with study
 
	
 
Review recruitment strategies
 
Report to TSC
 
Continue but modify and monitor closely
 
	
 
Recruitment not feasible
 
Decision not to proceed
 
		

 Table 3: Study stop-go criteria

Should a decision be made not to proceed, recruitment to the trial will stop but we will continue trial participation within the follow-up period for those already recruited.

#### Interim Review Point

As a result of the internal trial pilot, the Funder has requested a second review point on 1st December 2024.

#### **12.6 The Level of Statistical Significance**

Outcomes, collected in both treatment arms, will be considered statistically significant for p-values <0.05. There will be no adjustment for multiplicity, relevant results from other studies already reported in the literature will be taken into account to support the interpretation.

EndoNET\_Protocol\_V4.0\_21Aug2024

© Copyright: The University of Oxford and Oxford University Hospitals NHS Foundation Trust 2022 Page 64 of 84

## 12.7 Procedures for Reporting any Deviation(s) from the Original Statistical Plan

Any deviation(s) from the original statistical analysis plan will be described and justified in a revised version of the SAP.

## **12.8 Health Economics Analysis**

A within-trial analysis will be conducted to assess the cost-effectiveness of implementing NET followed by surgery and adjuvant ET compared with the current practice of surgery followed by adjuvant ET for reduction in mastectomy at 15 months. Resource utilisation, cost and cost-effectiveness of implementing NET followed by surgery and adjuvant ET compared with the current practice will be assessed, adhering to good economic evaluation practice with an NHS and Personal Social Services perspective (78, 79).

A detailed health economics analysis plan will be prepared in the first 4 months of the programme, setting out the proposed analyses in detail. The health economists will work with the project team and PPI group to identify and design the collection of health care resource use information and HRQoL. A self-complete health care use questionnaire will be used to collect all resource events associated with treatment and administering NET, side effects or complications and follow-up consultations in primary and secondary care settings. The self-completed health care use questionnaire will be administered at baseline (TO), 6 weeks (F1), 7 months (F2) and 15 months (F3) post randomisation to indicate health care resource use from 6 weeks prior to randomisation to baseline, baseline to 6 weeks, from 6 weeks to 7 months and from 7 to 15 months. Where possible, resource utilisation items will be valued using national unit cost schedules (e.g. NHS Reference costs) and medication costs calculated using British National Formulary pricing. Where unit costs are unavailable (e.g. intervention costs) bottom-up micro-costing will be undertaken. Number of work/usual activity days lost due to the treatment process and any related complications and any overthe counter medications purchased by participants will also be captured by the participant questionnaires. We will test for baseline difference in health care resource use between the trial arms and if required, adjust for these differences using the most appropriate recommended method. The impact of the inclusion of societal costs on the base-case cost effectiveness results will be explored in the sensitivity analysis. All costs and effects will be discounted at 3.5% following the guidelines from the National Institute for Health and Care Excellence (78).

To determine quality-adjusted life-years (QALYs), the EQ-5D-5L (80) will be used to measure HRQoL at baseline (T0), 6 weeks (F1), 7 months (F2) and 15 months (F3). Each time interval will be weighted by the utility scores apportioned to that time with linear interpolation between data collection time points. At present EQ-5D-5L responses would use a mapping algorithm/function to the EQ-5D-3L and the existing UK valuation set applied, in line with NICE recommendations, but an approved UK value set for the EQ-5D-5L may be available by the later stage of this trial. We will test for baseline difference in utilities between the trial arms and if required adjust for these differences using the most appropriate recommended method (81).

The health care use questionnaire and the EQ-5D-5L will be sent for self-completion via email but, if requested, they could be undertaken by mail. In some circumstances, where it is not feasible to complete questionnaires using our preferred method(s), participants may complete questionnaires over the telephone with their local NHS team. The central trial team may also contact participants by telephone to complete questionnaires and to remind participants to complete them if they are overdue.Incremental cost effectiveness ratios (ICERs; cost per QALY) will be estimated. Sampling uncertainty concerning

EndoNET\_Protocol\_V4.0\_21Aug2024

© Copyright: The University of Oxford and Oxford University Hospitals NHS Foundation Trust 2022 Page 65 of 84 estimated costs and quality adjusted survival observed in the trial, will be fully reported. Any remaining methodological uncertainty (e.g. discount rates, sources of unit cost information or future therapy costs) will be explored using sensitivity analysis. The ICERs will be compared against the threshold used to establish value for money in the NHS (currently in the region of £20,000 to £30,000 per QALY) (78).

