Participants in this randomised controlled trial are allocated by chance to one of two arms, which determines their treatment schedule. Endocrine therapy is usually started after surgery. However, all participants in both trial arms will start endocrine therapy (letrozole, anastrozole or exemestane) on joining the trial and prior to surgery. Therefore, they may have the opportunity to start treatment with endocrine therapy before they normally would. If patients start aromatase inhibitor endocrine therapy following their current diagnosis of breast cancer as part of routine care before the trial, this is allowed provided the endocrine therapy was not started more than 14 days prior to trial entry.

Participants in both arms have endocrine therapy for the same total length of time within the trial, but it is the timing of the surgery that differs. The type of surgery all participants will have will be determined by them and their clinical team as part of standard clinical care. Arm 1 will have surgery within 2-4 weeks (up to 8 weeks permitted for trial purposes) of starting their pre-surgical endocrine therapy; arm 2 will receive surgery after 6 months (+/-1 month) of pre-surgical endocrine therapy (neoadjuvant endocrine therapy;

EndoNET\_Protocol\_V4.0\_21Aug2024

© Copyright: The University of Oxford and Oxford University Hospitals NHS Foundation Trust 2022 Page 11 of 84 NET). Participants in Arm 2 will receive an ultrasound (USS) scan at 3 months and 5 months to closely monitor their response to this endocrine therapy prior to their surgery.

Patients with breast cancer, included as part of the study leadership team, and others have been extensively consulted in the trial design. They indicated preserving the breast and overall quality of life as the most important outcomes by which to measure study success.

The trial aims to recruit at least 792 women from at least 30 NHS hospitals across the UK. Participants in both arms will have their surgical treatments recorded and will complete quality of life questionnaires at intervals during their 15-month participation in the study. The results will be published in medical journals and presented at international conferences and updates of study progress will be available on the website and by study newsletter.

As part of this research, we are also running sub-studies to which patient participation is optional:

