## 9.10. Surgical treatment (Main Trial)

Since surgical treatments constitute the primary endpoint, and several of the secondary endpoints, these will be recorded in detail within the CRFs. Surgery to the breast will be mastectomy or breast conservation according to local protocols, national guidance and surgeon and patient agreement. Immediate breast reconstruction and oncoplastic procedures will also be performed as appropriate. Following breast conservation clear margins should be obtained. Margin involvement will be according to local and national protocols and if margins are considered involved re-excision should be performed.

Surgery to the axilla will also be according to local protocols, national guidance and surgeon and patient agreement. Sentinel node biopsy (SNB) should be performed where pre-operative staging indicate no axillary node involvement. Where axillary node involvement is confirmed pre-operatively SNB or axillary dissection is acceptable according to the clinical situation and local and national guidance. In the NET arm clip placement or others forms of localisation of axillary nodes confirmed to be involved pre-NET is acceptable according to local protocols and where required for targeted axillary dissection. Where the sentinel node shows evidence of involvement (micro or macrometastases) further treatment should be according to local and national protocols and can include monitoring, completion axillary clearance or radiotherapy.

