## 9.12. Radiotherapy

#### 9.12.1. Breast Radiotherapy

Radiotherapy, where required, should be given according to local protocols and national guidance. Consistent with NICE NG101 guidance for neo-adjuvant chemotherapy, both pre-treatment imaging findings as well as post-surgical histology should be considered in radiotherapy decision making in patients allocated to NET. Partial breast radiotherapy can be considered following breast conservation where tumour size is 3 cm or less on imaging at presentation and final histology. We note the recent adoption of a 5 fraction regimens nationally. The same radiotherapy fractionation protocol should be used for patients in both arms of the trial in individual centres.

Radiotherapy data will be collected on a dedicated CRF and will include information on whether the participant received radiotherapy, the type of radiotherapy and dosage. Further information related to the details of the radiotherapy given will also be recorded.

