## **11.4.** Reporting complications in relation to surgery

Any complications related directly to breast surgery and not considered related to AI treatment (example: prolonged hospitalisation, infection etc.) will not be part of the safety reporting but will be collected in the relevant trial CRF. These will be assessed using the Clavien-Dindo Classification of surgical complications.

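### Section 12.8 names a self-complete questionnaire as the source of all resource use; its fixed recall windows catch the surgical pathway differently by arm, although CRFs already record the main items

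*Protocol*

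**What the plan says.** Protocol section 12.8 (Health Economics Analysis) states the source of resource quantities: "A self-complete health care use questionnaire will be used to collect all resource events associated with treatment and administering NET". The sentence goes on to include side effects, complications and consultations in primary and secondary care. After the baseline form, the recall periods are "baseline to 6 weeks, from 6 weeks to 7 months and from 7 to 15 months". Objective 13, in the synopsis and in section 6.2, also names only the Health Care Use Questionnaire. The micro-costing in 12.8 concerns unit costs, not quantities.

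The timing of surgery differs by design. The lay summary says "Arm 1 will have surgery within 2-4 weeks (up to 8 weeks permitted for trial purposes) of starting their pre-surgical endocrine therapy", and "arm 2 will receive surgery after 6 months (+/-1 month) of pre-surgical endocrine therapy".

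Elsewhere the protocol records the main cost items on CRFs in both arms:
- Surgical treatments (section 9.10): "these will be recorded in detail within the CRFs".
- Radiotherapy (section 9.12.1): "Radiotherapy data will be collected on a dedicated CRF".
- Complications of breast surgery (section 11.4): these "will not be part of the safety reporting but will be collected in the relevant trial CRF".
- Adjuvant chemotherapy and other systemic therapy: section 10.1.5 also requires these on the CRF.
- Re-excision, advanced breast conservation and reconstruction: these are components of secondary outcome 9.

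Section 12.8 does not say that any of these records feed the costing.

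**The concern.** The questionnaire dates are fixed from randomisation, but the costly events are tied to surgery, which comes about five months later in the NET arm. A given step of the pathway therefore falls in a different recall window, at a different distance from the next form, depending on the arm. If women report less completely as the delay grows, the completeness of cost data will differ by arm for reasons unrelated to actual use. Greater loss in NET would imitate the reduction in surgical burden that the trial hopes to find; greater loss in control would hide it. Either would carry into incremental cost and into the cost per QALY that section 12.8 compares with £20,000 to £30,000.

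A second weakness does not depend on recall. If the questionnaire is the only source, a missed form removes a whole period of hospital costs for that woman, even though the CRFs may hold the operations and radiotherapy in question. Section 9.2 limits telephone chasing to two contacts.

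**Working it through.** **Inputs.** Forms at 6 weeks, 7 months and 15 months (section 12.8). Control surgery at 2-4 weeks, up to 8 weeks permitted; NET surgery at 5 to 7 months, target 6 (lay summary). One week = 7/30.4375 = 0.230 months. Two simplifications: endocrine therapy starts at randomisation, and forms are completed on their nominal dates.

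**Step 1: length of each window.**
- First: 6 × 0.230 = 1.38 months.
- Second: 7 − 1.38 = 5.62 months.
- Third: 15 − 7 = 8.00 months.

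**Step 2: delay from the index operation to the next form.** Delay = date of next form − date of operation.
- Control at 2 weeks: 1.38 − 0.46 = 0.92 months. Control at 4 weeks: 1.38 − 0.92 = 0.46 months.
- NET at 5, 6 and 7 months: 7 − 5 = 2.0, 7 − 6 = 1.0 and 7 − 7 = 0 months.
- Control just after 6 weeks: 7 − 1.38 = 5.62 months. Control at 8 weeks: 7 − 1.84 = 5.16 months.

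At target times the two arms are close. For permitted control surgery after week 6, the delay is longer in control.

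**Step 3: delay for an event d months after surgery**, with control surgery at 3 weeks (0.69 months) and NET surgery at 6 months.

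| d | Control | NET | NET − control |
|---|---|---|---|
| 0 | 0.69 | 1.00 | +0.31 |
| 1 | 5.31 | 0.00 | −5.31 |
| 1.5 | 4.81 | 7.50 | +2.69 |
| 3 | 3.31 | 6.00 | +2.69 |
| 6 | 0.31 | 3.00 | +2.69 |
| 8 | 6.31 | 1.00 | −5.31 |

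From just over 1 month to about 6.3 months after surgery, the control event waits for the 7-month form and the NET event for the 15-month form. The difference is constant: (15 − 6 − d) − (7 − 0.69 − d) = 9 − 6.31 = 2.69 months. Around 1 month and around 8 months after surgery the order is reversed. The NET event at d = 1 falls on the day of the 7-month form.

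**Step 4: late control surgery.** With control surgery at week 7 (1.61 months):
- Index operation: 7 − 1.61 = 5.39 months, against 1.00 in NET.
- Event at d = 1.5: 7 − 3.11 = 3.89 months, against 7.50 in NET.
- Event at d = 6: 15 − 7.61 = 7.39 months, against 3.00 in NET.

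The sign depends on the event and on when control surgery takes place.

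**Step 5: cost of a missed form.** If the questionnaire is the only source, the longest period lost is 8.00 months (the 15-month form), and the next longest is 5.62 months (the 7-month form).

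**The case against.** The strongest reply is that reliance on the questionnaire alone is inferred. Section 12.8 does not exclude CRF data. It defers the detailed analyses to a health economics analysis plan, which is not shown and may already cost surgery from the CRFs. Section 13.3.1 lets sites check hospital records for admissions, section 9.16 keeps capturing admissions after withdrawal, and section 12.8 allows telephone reminders and telephone completion. Part of this stands: actual practice may be better than the text. But the text is not silent. It assigns all resource events to one source and names no other, so the protocol as written describes the weaker method.

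A reader might also infer that NET will look cheaper than it is, because at target times each stage of the pathway falls in a longer window in NET (for the operation, 5.6 against 1.4 months, about four times as long). The documents do not support this. Window length is not recall delay: the delay for the operation is about equal at target, and step 4 shows it reversed for late control surgery. An illustration shows how fragile the direction is. Assume a reporting probability of exp(−λ × delay in months) and five equally weighted events at 0, 1.5, 2.5, 3 and 6 months after surgery. For λ = 0.02, 0.05 and 0.10, the share reported is 0.95, 0.88 and 0.78 in control (surgery at 3 weeks), against 0.91, 0.79 and 0.64 in NET. Moving control surgery to week 7 lowers the control shares to 0.92, 0.81 and 0.66, and the gap nearly closes. Neither the curve nor the weights come from the documents, so no amount in pounds or QALYs can be given.

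**Conclusion.** The point holds as a weakness in the stated method. The recall windows of 1.4, 5.6 and 8.0 months cover the surgical pathway differently by arm. At surgery times of 3 weeks and 6 months, the reporting delay is about 2.7 months longer in NET for events roughly 1.5 to 6 months after surgery, about equal for the index operation, and reversed for some other events. Differential under-reporting is therefore possible. Its direction and size are not known from the documents; it would arise only if reporting falls off with delay and if the questionnaire really is the only source. Under that second condition, a missed form also loses up to 8 months of hospital costs, whatever the recall error. Costing the main items from records that the trial already keeps is the better method even if recall error is nil.

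**What to change.** State in section 12.8, and in the health economics analysis plan, that operations, re-operations, reconstruction, surgical complications, radiotherapy and adjuvant systemic therapy are costed from the trial CRFs in both arms. Use hospital records for admissions and length of stay where available; the protocol does not show that routine length of stay is a CRF field, so this should be checked. Give the CRF precedence where both sources record an item. Keep the questionnaire for primary and community care, other outpatient contacts, over-the-counter purchases and days lost.

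The cost is wording, linkage of CRF items to unit costs, and some de-duplication. The items that the protocol already places on CRFs need no new visits, patients or forms. If the health economics plan already works this way, only the sentence in 12.8 needs to be aligned with it.
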